9.8. Assessment of Safety

Safety will be assessed by monitoring the occurrence of adverse events (AEs), serious adverse events (SAEs), death, adverse device effects (ADE), unanticipated serious adverse device effects (USADE), device deficiency/malfunction, and/or device misuse. Assessments will take place during the procedure through post-operative day 30 (+14 days) and will be recorded in the eCRF.

9.9. Recording Data

[figure not shown]
This study will utilize an electronic database and eCRF. All data requested on the eCRF are required. Study visits or measurements not collected and/or recorded will be considered deviations unless otherwise specified. The Principal Investigator or authorized designee(s) must ensure the accuracy and completeness of the recorded data and then provide his/her electronic signature on the eCRFs. The Investigator's electronic signature for specific eCRFs will be documented in compliance with local regulations and compliance with the protocol. Changes to data previously submitted to the sponsor will require a new electronic signature by the Investigator to acknowledge/approve the changes.

9.10. Deviation Handling

The Investigator is not allowed to deviate from the CIP, except under emergency circumstances to protect the rights, safety and well-being of human subjects, otherwise no changes to the protocol will be permitted without the written approval from Medtronic, the IRB/EC and Competent Authority. The investigator must notify Medtronic and the reviewing IRB/EC of any deviation from the Investigational Plan. The deviation will be recorded in the eCRF and such notice must be given as soon as possible, but in no event later than 5 working days after the emergency has occurred. Except in such an emergency, prior written approval by Medtronic is required for changes in or deviations from the Plan. If these changes or deviations affect the scientific soundness of the Plan or the rights, safety, or welfare of human subjects the IRB/EC will also be notified. All other deviations will be reported per the site's IRB/EC deviation policy. Should any deviations from the Investigational Plan occur, these will be reviewed by Medtronic for their clinical significance and compliance to the protocol. Repetitive or serious investigator compliance issues may result in the need to initiate a corrective action plan, and in some cases, freeze enrolment or ultimately terminate the Investigator's participation in the clinical study.

If it is discovered that an investigator is not complying with the signed Investigator Agreement, the investigational plan, applicable laws, or any conditions of approval imposed by the reviewing IRB/EC, the monitor will report to the Sponsor and take such steps necessary to promptly secure compliance. If compliance cannot be secured, device shipments to the investigator may be discontinued and the investigator's participation in the investigation terminated. The monitor shall also require such an

MDT17025SIG Version 3.0 Page 35 of 57

investigator to dispose of or return the device, unless this action would jeopardize the rights, safety, or welfare of a subject.

9.11. Subject Withdrawal or Discontinuation

9.11.1. Enrolled

A subject is considered enrolled in the study when it is confirmed they meet inclusion and exclusion criteria and ICF is signed and dated by subject and the Investigator and must be followed for the full 30 days if the procedure was begun or completed with the study device. Enrollment can take place 30 days before procedure and subjects will be followed for 30 (+14) days postoperative. If enrollment occurs greater than 30 days prior to procedure the subject will require to be reconsented.

9.11.2. Screen Failure

Subjects who provide study consent, but then are determined to be ineligible prior to the procedure with the study device will be considered a screen failure and will not require additional study follow-up visits. The reason for the screening failure will be clearly delineated on the applicable eCRFs.

9.11.3. Discontinuation

Subjects who provide study consent, and are deemed eligible, but for which do not undergo the procedure with the study device will be considered "discontinued" and will be followed until discharge. These subjects will only contribute AE data intra-operatively until discharge (no additional follow-up). Follow up of subjects withdrawn or discontinued will be determined by investigator. Safety and device deficiency data will not be collected from the discontinued population.

[figure not shown]

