9.7. Assessment of Efficacy

Primary assessment will examine the incidence of subjects reporting serious adverse device effects up to and including 30 (+14) days postoperative and device deficiencies/malfunctions affecting the intended

MDT17025SIG Version 3.0

Page 32 of 57

performance will be recorded in the eCRF and used to assess the efficacy of the Signia™ stapling system. In addition, the following assessments will be collected:

9.7.1. **Operative (Day 0)**

The Study Investigator should perform the surgical procedure according to the appropriate standard procedures and practices at his/her institution using the Signia™ Stapling System. Additionally, the following procedures and assessments will be performed:

- Eligibility Criteria*
- Vital signs (heart rate, temperature, respiratory rate, blood pressure, pulse, oxygen saturation levels)*
- Abbreviated physical exam, including height, weight, and examination of the heart, lung, and abdomen*
- American Society of Anesthesiologists (ASA) grade (See Appendix B, Section 18.2)
- Serum or urine pregnancy test females of child bearing potential (USA only) or per EU local requirements *
- * Assessments only need to be repeated if Screening/Operative Visit occur on different days
 - Operative date
 - Operative start (skin incision) and stop times (skin closure)
 - Type of procedure
 - General anesthesia information (type, start and stop times)
 - Study device data (i.e., type of reload used, staple size, lot number of devices used, number of firings, location of firings)
 - Use of Signia feedback display (if applicable)
 - Relevant concomitant medications (only those related to relevant medical history or adverse events will be collected e.g.: anticoagulants, blood pressure, antibiotics, pain medications)
 - Procedure related adverse events
 - Adverse device effects (ADEs) (ADEs, as defined by ISO14155-2011, see section 11.1.3 for additional details)
 - Staple line assessment
 - Device deficiencies/malfunctions affecting intended performance to include but not limited to;
 - System set-up (insertion guide, power shell)
 - Organic light emitting diode (OLED) screen display
 - Rotation
 - Articulation
 - Clamp/UnClamp
 - Firing
 - Use of manual retraction tool

MDT17025SIG Version 3.0 Page 33 of 57

- User errors
- Unintended cutting
- Insufficient staple deployment
- o Inability to complete the firing sequence
- Stapling without cutting
- Device accountability

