11.1.6. Device Deficiencies

In alignment with ISO14155:2011 (Section 3.15), a Device deficiency is an inadequacy of a medical device-related to its identity, quality, durability, reliability, safety or performance; such as malfunction, misuse or use error and inadequate labeling.

All Signia™ Stapling System device deficiencies/malfunctions will be documented on the Device Deficiency/Malfunction eCRF.

In the event of a device deficiency the device should be returned to Covidien for analysis, if possible. Instructions for returning the study device will be provided. Device deficiencies should also be documented in the subject's medical record.

Device deficiencies are NOT to be reported as AEs.

However, if there is an AE that results from a device deficiency, that specific event would be recorded on the appropriate eCRF.

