11.2. Reporting of Adverse Events

The following events are generally considered reportable during the course of this study and should be reported to the sponsor:

any device related AE, SADE, SAE, or USADE

- any Device Deficiency/Malfunction that might have led to a SADE if
 - o suitable action had not been taken or
 - o intervention had not been made or
 - o if circumstances had been less fortunate
- new findings/updates in relation to already reported events.

Events will be reviewed by the sponsor to determine any reporting obligations to National Competent Authorities and IRBs/ECs.

The following table captures the reporting requirements for this study. Local and regional regulatory requirements shall be followed in addition to study requirements.

Type of Event	Timeframe	Submit to
Any Death	As soonas practicable but no more than 10 work days after the day that you become aware of information from any source, that reasonably suggests that a device has or may have caused or contributed to the death of a patient of your facility	Sponsor/ Device Manufacturer and Local (IRB/EC) and regional regulators (FDA)
UADE	As soonas possible, but in no event later than 10 working days after the investigator first learns of the effect.	Sponsor / Device Manufacturer and any local/ regionally required regulators
All Serious Events including SAEs, USADEs, Serious Injuries or Significant Safety Issues	Within 24 hours, but no later than 10 work days (and/or per local requirements) after the day that investigator becomes aware of information, from any source, that reasonably suggests that a device has or may have caused or contributed to a serious injury to a patient of your facility.	Sponsor / Device Manufacturer and as per local reporting requirements.

MDT17025SIG Version 3.0 Page 45 of 57

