13.3. Analysis Population

The full analysis set (FAS) will consist of all enrolled and treated subjects (using Signia[™]). For this study the full analysis set corresponds to the safety population. FAS will serve as the primary analysis population for safety and performance analyses, as well as for demographics and baseline data analysis.

MDT17025SIG Version 3.0 Page 48 of 57

The per protocol (PP) population will consist of all subjects from the FAS population who do not have a major protocol violation. Analyses on the PP population will provide supporting evidence to the primary results (obtained on FAS).

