7.1.3. Analysis Sets

SIGNIA Statistical Analysis Plan	
Version [Final#1.0] Page 12 of 15	Medtronic

Full Analysis Set (FAS): includes all enrolled and treated subjects (using Signia[™]). For this study, the Full analysis set corresponds to the safety population. FAS will serve as the primary analysis population for safety and performance analyses, as well as for demographics and baseline data analysis.

The per protocol Analysis Set (PPAS): includes all subjects from the FAS population who do not have a major protocol violation. Analyses on the PPAS will provide supporting evidence to the primary results (obtained on FAS).

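### Protocol 9.11.3 bars device-deficiency data from subjects in whom Signia was not used, contradicting 11.1.6 and 11.2, so a set-up failure ending in no use can go unrecorded and uncounted

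*Protocol*

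**What the plan says.** **On collection.** Protocol 9.11.3 defines discontinued subjects as those who consent and are eligible but do not have the procedure with the study device. Of them it says: "Safety and device deficiency data will not be collected from the discontinued population". The same paragraph has these subjects contribute adverse event data up to discharge.

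Two later sections set no such limit. Protocol 11.1.6 says that all Signia "device deficiencies/malfunctions will be documented on the Device Deficiency/Malfunction eCRF". Protocol 11.2 makes device-related adverse events and serious adverse events reportable, together with "any Device Deficiency/Malfunction that might have led to a SADE if" events had gone less well.

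Protocol 9.7.1 lists system set-up and the OLED display among the deficiencies to be recorded on the operative day.

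**On follow-up.** Protocol 8.2 and 9.11.1 say that an enrolled subject "must be followed for the full 30 days if the procedure was begun or completed with the study device".

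**On analysis.** The full analysis set (FAS) "will consist of all enrolled and treated subjects" in whom Signia was used (Protocol 13.3); under SAP 7.1.3 it likewise "includes all enrolled and treated subjects". The per-protocol set is a subset of the FAS. SAP 7.9 names device deficiency or malfunction as the secondary endpoint and analyses it on these two sets. Protocol 13.4.2 plans counts and percentages for it, and SAP 7.2 runs analyses by arm. SAP 7.1.1 tabulates reasons for discontinuation on the FAS.

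**The concern.** A powered stapler can fail before it touches tissue: the power shell does not seat, or the screen does not work. If the surgeon then completes the operation with something else, the subject fits the 9.11.3 definition of discontinued, and does so because the device failed. Whether the failure is counted then depends on the failure itself.

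The study is meant to confirm performance as well as safety, and a device that could not be used is a performance failure. Under 9.11.3 a site may leave it off the eCRF; under 11.1.6 it must enter it. No text says which instruction prevails. If the event is entered, the analysis sets still drop it. The reason for non-use is lost from the tables too, because the FAS on which discontinuation reasons are tabulated cannot contain an untreated subject.

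At stake is a one-directional understatement of a named secondary endpoint. A lesser matter is the conflicting instruction on collecting adverse events in the same subjects.

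**Working it through.** **1. The texts side by side.** Consider a subject whose set-up failed and in whom Signia was not used.

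| Question | Text | Answer |
|---|---|---|
| Is the deficiency recorded? | Protocol 9.11.3 | No |
| | Protocol 11.1.6 | Yes, all deficiencies |
| | Protocol 11.2 | Reportable, if it might have led to a SADE |
| Are adverse events recorded? | Protocol 9.11.3, AE sentence | Yes, until discharge |
| | Protocol 9.11.3, final sentence | No safety data |
| | Protocol 11.2 | Device-related events reportable |
| Is the subject in the FAS? | Protocol 13.3, SAP 7.1.3 | No, not treated with Signia |
| Does the event enter the secondary analysis? | SAP 7.9 | No, FAS and per-protocol set only |

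The conflict with 11.1.6 covers every deficiency. The conflict with 11.2 is narrower on deficiencies: only those with SADE potential.

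**2. Direction.** Let N be the subjects in whom Signia was attempted, D those with a deficiency, and k those among the D whose failure ended in no use. The per-attempt rate is D/N. The plan reports (D − k)/(N − k). The difference is

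D/N − (D − k)/(N − k) = k(N − D) / [N(N − k)],

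which is never negative. The reported rate cannot exceed the per-attempt rate.

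**3. Size.** The plan states no deficiency rate, so there is no planned figure to reproduce. The sample sizes of 127, 53 and 74 are from Protocol 13.2. D and k are not in the documents and are assumed here, with set-up attempted in every subject.

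| N | D | Per-attempt rate | k | Rate as planned |
|---|---|---|---|---|
| 127 | 5 | 3.9% | 1 | 4/126 = 3.2% |
| 127 | 5 | 3.9% | 2 | 3/125 = 2.4% |
| 127 | 5 | 3.9% | 3 | 2/124 = 1.6% |
| 127 | 8 | 6.3% | 1 | 7/126 = 5.6% |
| 127 | 8 | 6.3% | 2 | 6/125 = 4.8% |
| 127 | 8 | 6.3% | 3 | 5/124 = 4.0% |
| 53 (abdominal) | 2 | 3.8% | 1 | 1/52 = 1.9% |
| 74 (thoracic) | 3 | 4.1% | 1 | 2/73 = 2.7% |

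With all subjects combined, each case costs about 0.8 percentage points: for D = 5 and k = 1, 122/(127 × 126) = 0.76%. In a single arm one case weighs more, 1.8 points in the abdominal row and 1.3 in the thoracic row.

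If the only two deficiencies are both no-use failures, the plan reports 0/125 (exact 95% CI 0 to 2.9%), whereas 2/127 = 1.6% (0.2% to 5.6%) occurred. If k = 0 there is no effect.

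**The case against.** **Other records may catch the event.** Protocol 9.11.4 puts the reason for study exit on the eCRF, 11.1.6 also calls for an entry in the medical record and return of the device where possible, 7.11 logs malfunctioning devices, and complaints go to post-market vigilance. This stands as far as knowledge of the event goes. None of these routes feeds the analysed endpoint.

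**Such cases should be rare.** Protocol 7.1.3 supplies about two power handles per site. A fault remedied with a spare leaves the subject treated and in the FAS, so only complete abandonment of Signia matters. This stands, and it makes k smaller. It also makes the larger illustrations strained: k = 3 of D = 5 means that 60% of all deficiencies ended in no use.

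**No per-subject deficiency proportion is spelled out.** SAP 7.9 itemises mainly staple-line outcomes and readmissions, and the endpoint carries no acceptance criterion. It is true that no pass/fail decision depends on the rate. But the endpoint is named as device deficiency or malfunction, and Protocol 13.4.2 plans counts and percentages for it.

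**A failed set-up may count as the procedure having begun.** The subject would then be followed and arguably not be discontinued. The documents do not say, and FAS membership would still be unclear because the subject was not treated with Signia.

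**Enrolled minus FAS is visible in the disposition summary of SAP 7.1.1.** That bounds k from above but does not say why subjects were untreated.

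**An extra analysis set is more than is needed.** A listing would show the cases, but not a rate with the right denominator.

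**Conclusion.** The point holds. As written, Protocol 9.11.3 contradicts 11.1.6, the device-related parts of 11.2, and its own sentence on adverse events. Separately, the analysis sets leave a no-use set-up failure out of the deficiency results even when a site records it.

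The direction is certain: any such case favours the device. The size is unknown, because it depends on an assumed k; about 0.8 percentage points per case overall, and more within an arm, is the scale to keep in mind.

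Malfunctions after the procedure was begun with Signia are retained. The primary SADE analysis and its 20% criterion are not claimed to be affected. The change should be made because the contradiction is plain and the remedy is small, not because a large bias has been shown.

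**What to change.** **Protocol.** Delete the quoted sentence in 9.11.3 and reconcile the section with 11.1.6 and 11.2, so that deficiencies and adverse events are recorded for every subject in whom Signia set-up or use was attempted. State in 8.2 and 9.11.1 whether a failed set-up counts as the procedure having begun with the device.

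**SAP.** Keep the FAS as it is for the primary and staple-line analyses. In 7.1.3 and 7.9 add an attempted-use set (set-up started in the operating room), used for device deficiencies only. List any device-related adverse events in subjects with attempted set-up but no use. In 7.1.1 tabulate reasons for non-use and discontinuation on all enrolled subjects.

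**Cost.** One sentence deleted and one clarified in the protocol; one extra analysis set, a short listing and one changed disposition table in the SAP. The existing deficiency eCRF serves. The reported deficiency rate may come out slightly higher.

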9.11.4. Withdrawal

The reason for study exit, including screen failure, will be documented on the applicable electronic case report form (eCRF). In the event the subject withdraws consent during the study, the date of withdrawal will be documented. If the Study Investigator voluntarily removes a subject from further study participation, supporting documentation must be in place for the rationale and date of removal. Follow up of subjects withdrawn or discontinued will be determined by investigator.

9.11.5. Lost to Follow-up

Every attempt will be made to contact subjects that are noncompliant with study procedures. Subjects will be considered lost to follow-up once the following steps have been taken:

MDT17025SIG Version 3.0 Page 36 of 57

- Two phone calls should be made to the subject. Each attempt should be clearly documented in the source documents and the response or lack thereof should be captured.
- If there is no response to the phone calls, then an official, certified letter should be written to the subject. A copy of the letter and return or delivery receipts should be retained in the subject's source document.
- When all due diligence attempts to contact have been made, after a period of two (2) weeks, the subject will be considered Lost to Follow-up. The Sponsor must be notified and the End of Study (EOS) form must be completed.

10. Risks and Benefits

10.1. Potential Risks

Surgeons participating in this study are experienced with the known risks related to standard of care for abdominal and thoracic surgeries. Risks associated with participation in the clinical investigation and use of the Signia™ Stapling System with approved reloads in abdominal and thoracic procedures include, but are not necessarily limited to: adhesions, air leak, anastomotic leakage, atelectasis, bile leak, biliary fistula, bleeding, bronchopneumonia, cardiac complications, death, gastric leak, heart failure, hematoma, infection, inflammation, intra-abdominal fluid collection, liver failure, pleural effusion, pneumothorax, pulmonary embolism, stricture, ulceration, and wound dehiscence.

The instructions for use (IFU) will guide surgeons on proper use of the device. Surgeons and site staff will undergo training on the device prior to participation in the study.

Animal studies to evaluate the potential for AEs on reproductive ability and effects on the embryo/fetus have not been conducted. As with any device, there is always a risk of a rare or previously unknown side effect developing from the treatment or use of the device.

The risk analysis reports are based on the operation of Signia™ Stapling System by trained personnel. According to the Risk Analysis Chart, there were no unacceptable residual risks in the Zone 3 category (red) proceeding mitigation activities. The following are all residual risks that exist in a Zone 2 category (yellow) proceeding mitigation activities for the Signia™ Stapling System. These risks do not directly result from design or manufacturing failures, so the risk has been reduced as far as possible with appropriate mitigation controls in place:

- Non-sterile product
- EtO Residuals
- Exposure to Bio-Hazard
- Difficult Insertion through Port or Organ
- Non-functional Staple Closure (identified Intra- or Post- Operatively)

MDT17025SIG Version 3.0 Page 37 of 57

- Unintentional Firing
- Device Cuts without Stapling
- Reload Locks on Tissue
- Uncontrolled Rotation or Articulation
- Loss of Tissue Sensing Speed Control
- Reload De-articulates when Clamped on Tissue

The overall residual risk after design risk mitigation strategies and/or design control was deemed acceptable in the Risk Management Reports for the Signia™ Stapling System.

10.2. Potential Benefits

The information obtained from this study will be used to confirm the safety and performance of the Signia™ Stapling System. This information may or may not lead to findings that could result in a reduction of complications for future patients.

10.3. Risk-Benefit Rationale

A positive risk/benefit ratio has been demonstrated with the Signia™ Stapling System with appropriate reloads as evidenced by preclinical and biocompatibility testing.

[figure not shown]
The Signia™ Stapling System is a class II FDA 510K cleared product, and a MDD class IIa and class I CE-marked product. Consequently, the Signia™ Stapling System presents a favorable risk/benefit ratio to the subject. The instructions for use (IFU) in addition to surgeon training, will instruct surgeons on proper use of the device to mitigate risk. There are currently no known interactions between the Signia™ Stapling System and concurrent medical interventions.

11. Adverse Events and Device Deficiencies

Adverse event (AE) definitions used in this study are based on ISO 14155:2011 (Clinical Investigation of Medical Devices for Human Subjects -- Good Clinical Practice).

Foreseeable adverse events and anticipated adverse device effects can be found in the instructions for use. The instructions for use (IFU) in addition to surgeon training, will instruct surgeons on proper use of the device to mitigate these risks.

MDT17025SIG Version 3.0 Page 38 of 57

